3. GENERAL INFORMATION

Objective	To determine the percentage of subjects satisfied (Completely Satisfied or Very Satisfied) with vision after Phorcides Planned Contoura LASIK. The hypothesis is that a high percentage of subjects receiving the Phorcides Planned Contoura LASIK will be satisfied with their vision		
	Phorcides Planned Contoura LASIK will be satisfied with their vision.		
Test Article(s)	WaveLight® EX500 Contoura laser		
Control Article(s)	None.		
Sample size	104 eyes of 52 subjects		
Study Population	Subjects 21 to 39 years of who are appropriate candidates for laser refractive surgery.		
Number of sites	One		
Study Design	Single site, single-arm, prospective, observational study		
Masking	None		
Variables	Primary: Percentage of subjects satisfied (Completely Satisfied or Very Satisfied) with vision after Phorcides Planned Contoura LASIK based on PROWL Questionnaire preoperative vs postoperative (question #1 only).		
	Secondary:		
	• Percentage of eyes with post-op spherical equivalent within +/- 0.50 D.		
	 Exploratory: Preoperative and postoperative higher order aberrations (spherical aberration and coma). Preoperative and postoperative responses on the PROWL questionnaire (Q2-Q33). Preoperative and postoperative OSDI scores. Correlation of postoperative OSDI score and responses on the postoperative PROWL questionnaire (Q1). 		
Duration / Follow-up	Preoperative to 3 months postoperative		

The study will be registered with clinicaltrials.gov.

The study will be conducted in compliance with the protocol, GCP and applicable regulatory requirements

4	TARLE	OF	CONTENTS
H .	IADLL	UF	CONTENTS

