5. INTRODUCTION

Phoreides reproducibly and accurately applies geographic imaging software to topographic corneal measurements, utilizes optical physics of lens theory, and the refractive effect of treating corneal irregularities.^{1,2} It allows for a vector analysis that accounts for anterior corneal astigmatism, posterior corneal astigmatism, manifest refraction measured astigmatism, and internal astigmatism into a suggested topography-guided treatment. Combining all these vectors and compensating for the postoperative spherical effect that can be directly impacted by the ablation profile of the corneal higher order aberrations yields a mathematical based surgical plan for the suggested treatment of the patient's refractive spherical magnitude, the astigmatic magnitude, and the astigmatic axis. Consequently, it is anticipated that Phoreides will prove to be a powerful surgical planning tool directly resulting in improved postoperative patient satisfaction with visual acuity and visual symptoms.

The decision to choose between a Phorcides derived Contoura LASIK ablation versus other various refractive procedures often times can be a difficult decision because of a lack of previous research analyzing patient satisfaction with their postoperative uncorrected visual acuity and visual symptoms. The purpose of this study is to determine the percentage of subjects satisfied with vision after Phorcides Planned Contoura LASIK.

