6. OBJECTIVE(S)

To determine the percentage of subjects satisfied (Completely Satisfied or Very Satisfied) with vision after Phoreides Planned Contoura LASIK.

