8. STUDY DESIGN

8.1. Study Design

This study is a single site, single-arm, prospective, observational study of subject satisfaction, after successful bilateral LASIK surgery. Subjects will be assessed pre-operatively, operatively and at 1 week, 1 month, and 3 months post-operatively. Clinical evaluations will include measurement of visual acuity, manifest refraction, and topography, aberrometry, and administration of the OSDI and PROWL questionnaires.

The primary outcome measure will be the percentage of subjects satisfied (Completely Satisfied or Very Satisfied) with vision after Phorcides Planned Contoura LASIK based on PROWL Questionnaire preoperative vs postoperative (question #1 only).

Secondary outcome measures are as follows:

• Percentage of eyes with post-op spherical equivalent within +/- 0.50 D.

Exploratory outcome measures are as follows:

- Preoperative and postoperative higher order aberrations (spherical aberration and coma).
- Preoperative and postoperative responses on the PROWL questionnaire (Q2-Q33).
- Preoperative and postoperative OSDI scores.
- Correlation of postoperative OSDI score and responses on the postoperative PROWL questionnaire (Q1).

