9.2.2. Operative (Surgery)

All subjects will undergo bilateral LASIK surgery. The surgeon's usual standard of care with regard to treatment and medication will be used for all study subjects. Surgery planning will be performed using the surgeon's preferred method.

Any adverse events/serious adverse events (AEs/ SAEs) occurring during surgery will be noted at this visit. Any other problems during surgery and comments regarding surgery will be documented.

Any subject whose surgery is not completed successfully will be documented in the appropriate case report form. These subjects will be monitored for safety but clinical performance data may be excluded from the analysis.

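### The hypothesis of a high satisfaction percentage has no number or decision rule, and the primary variable, the sample size and the analysis do not agree on whether a level or a change is tested

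*Combined protocol and SAP*

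**What the plan says.** - **Hypothesis (section 3):** "The hypothesis is that a high percentage of subjects receiving the Phorcides Planned Contoura LASIK will be satisfied with their vision".
- **Objective (section 6):** "To determine the percentage of subjects satisfied (Completely Satisfied or Very Satisfied) with vision after" the procedure. This is a postoperative level, and section 6 states no hypothesis.
- **Primary variable (sections 3 and 8.1):** it opens with the percentage satisfied after surgery, then adds that this is "based on PROWL Questionnaire preoperative vs postoperative (question #1 only").
- **Sample size (section 11):** 46 pairs for 90% power at the 5% level to detect a mean paired difference of 25 points with a standard deviation of 50 points; 52 are enrolled to allow for dropout.
- **Analysis (sections 10.2, 10.2.1 and 10.3):** number and percentage for categorical variables; a paired t-test for continuous variables only; alpha of 0.05 for any test.
- **Design (section 3):** "Single site, single-arm, prospective, observational study", with no control article.
- **Introduction (section 5):** "The purpose of this study is to determine the percentage of subjects satisfied with vision after Phorcides Planned Contoura LASIK". The same section also says that "it is anticipated that Phoreides will prove to be a powerful surgical planning tool directly resulting in improved postoperative patient satisfaction" and motivates the work by "The decision to choose between a Phorcides derived Contoura LASIK ablation versus other various refractive procedures".
- **Surgery (section 9.2.2):** "Surgery planning will be performed using the surgeon's preferred method".

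**The concern.** A hypothesis that a percentage will be high can be tested only if high has a value and there is a rule for comparing the result with it. The plan has neither, so the judgement is left to whoever reads the final percentage.

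The before/after wording adds a second possible question, and the two can give different answers. As invented illustrations, a move from 40% to 70% satisfied is a clear gain that may not be high, while 90% to 92% is high with almost no gain. The plan does not say which reading decides.

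There is also a risk in interpretation. The introduction anticipates a direct effect of the planning software, but one arm observed before and after surgery cannot separate the software from LASIK itself. Section 8.2 says that no bias is expected because the study has a single arm, so this limit is not acknowledged. A favourable percentage could be credited to the software without support from the design.

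**Working it through.** **1. What each part of the plan addresses**

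| Place | Quantity | Number or rule |
|---|---|---|
| Section 3, hypothesis | Postoperative percentage | None |
| Section 6, objective | Postoperative percentage | None (estimation) |
| Sections 3 and 8.1, primary variable | Postoperative percentage, qualified as before vs after | None |
| Section 11, sample size | Mean paired change in points | 25 points, SD 50 |
| Section 10.2, categorical outcome | Counts and percentages | No interval, no test |
| Section 10.2.1, paired t-test | Continuous variables | Does not cover a binary outcome |

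The only numeric target is a change in points. It is a planning assumption and is not tied to the hypothesis.

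**2. The plan's own sample size**

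Inputs from section 11: difference 25, SD 50, so d = 25/50 = 0.5; power 0.90; alpha 0.05, taken as two-sided because sidedness is not stated.

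- Normal approximation: n = (1.960 + 1.282)² / 0.5² = 42.03, so 43.
- Noncentral t: n = 44. Power at 46 is 0.913.
- Dropout: 1 − 46/52 = 11.5%. An assumed 10% also leads to 52, since 46/0.90 = 51.1.

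The stated 46 is within two subjects of 44. The arithmetic is acceptable, but it sizes a mean change and not a postoperative level.

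**3. What 46 evaluable subjects can show about a level**

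Requiring the exact two-sided 95% lower limit to exceed a value p0 is the same as an exact binomial test at one-sided 2.5%. The smallest passing count r satisfies P(X ≥ r | 46, p0) ≤ 0.025, and power is P(X ≥ r | 46, p1). The documents give neither p0 nor p1; both are assumed ranges.

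| Assumed value for high (p0) | Needed | Power if true rate 90% | Power if true rate 95% |
|---|---|---|---|
| 60% | 35/46 | 0.998 | 1.000 |
| 70% | 39/46 | 0.916 | 0.998 |
| 80% | 43/46 | 0.312 | 0.803 |
| 85% | 44/46 | 0.148 | 0.594 |

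**4. Precision if the study is estimation only**

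Exact (Clopper-Pearson) 95% intervals at 46:

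- 37/46 (80.4%): 66.1% to 90.6%
- 41/46 (89.1%): 76.4% to 96.4%
- 44/46 (95.7%): 85.2% to 99.5%

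Under the present wording, each of these could be reported as high.

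**5. The before/after reading as a binary comparison**

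Assume that the 25 points are percentage points and the SD of 50 is on a 0/100 scale. The discordant proportion is then 0.50² + 0.25² = 0.3125, split as (0.3125 + 0.25)/2 = 0.28125 improving and (0.3125 − 0.25)/2 = 0.03125 worsening. Exact McNemar power is 0.876 at 46 and 0.920 at 52. A paired binary comparison is thus feasible as a secondary analysis, although the plan does not name one.

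**The case against.** The strongest reply is that this is a descriptive study and should be read as one. Section 6 gives only an estimation objective, section 5 states a descriptive purpose, and no objective, endpoint or analysis compares planning methods. A single-arm estimate is legitimate. On this view the fault is one vague adjective in the synopsis. Much of that stands, and it rules out several stronger readings:

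- A reader might infer that the study sets out to show that Phorcides planning is better than other procedures and fails by design. The documents do not support this. The choice between procedures is background, and the effect of the software is anticipated, not set as an objective.
- A reader might infer that the endpoint is purely a before/after change. It is not: the primary variable opens with the postoperative percentage, and the before/after phrase is an ambiguous qualifier.
- A reader might infer that the sample size is wrong. It reproduces closely; it answers a different question.
- A reader might want high set at the satisfaction rate of the LASIK study cited in section 11, to be exceeded by the lower confidence limit. That rate is not in the documents, and the rule would in effect be a superiority test against historical LASIK. If the true rate only equalled the reference, the chance of passing would be at most 2.5%.

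What the reply does not remove is that section 3 does state a hypothesis, section 11 does size a test at 5%, and nothing connects the two.

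**Conclusion.** The concern holds in limited form. The hypothesis has no value or decision rule, the primary variable is ambiguous between a level and a change, section 11 sizes the change, and the binary endpoint has no interval or named test. Followed as written, the plan leaves the hypothesis to be judged after the data are seen.

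The size of the problem depends on the missing number. With 46 evaluable and a true rate of 90%, power runs from 0.916 against 70% to 0.148 against 85%; with a true rate of 95%, from 0.998 to 0.594. These rates are assumptions.

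To say that any result would count as a success goes too far: the documents define no success claim beyond the hypothesis in section 3. On attribution, the point is a limit on the conclusion to be written into the plan, not a fault in choosing a single-arm descriptive design.

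**What to change.** Before enrolment:

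1. In sections 3, 6, 8.1 and 10.2, make the percentage satisfied on question 1 at Visit 5 the primary measure, reported with an exact 95% confidence interval. Make the paired preoperative-to-postoperative change in question 1 secondary.
2. Choose one of two routes. Either state the numeric value that counts as high, require the lower 95% limit to exceed it, and show the power at 46 evaluable for that value; or drop the hypothesis and present the study as estimation only.
3. Restate section 11 to match, as power for the chosen value or as expected precision at 46 evaluable.
4. State that conclusions are limited to satisfaction after this procedure in this single-arm population and do not attribute it to the planning software.
5. Reconcile section 9.2.2, which leaves planning to the surgeon's preference, with the description of the procedure as Phorcides planned in sections 3, 6 and 8.1.

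Cost: Table 15.1 already schedules the questionnaire at Visits 1 and 5, so the change itself needs no new data or subjects. A value for high at which 46 subjects have low power would have to be accepted openly as such. The hypothesis can then fail or is dropped, the permitted conclusion is narrower, and section 11 must be rewritten.

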5. INTRODUCTION

Phoreides reproducibly and accurately applies geographic imaging software to topographic corneal measurements, utilizes optical physics of lens theory, and the refractive effect of treating corneal irregularities.^{1,2} It allows for a vector analysis that accounts for anterior corneal astigmatism, posterior corneal astigmatism, manifest refraction measured astigmatism, and internal astigmatism into a suggested topography-guided treatment. Combining all these vectors and compensating for the postoperative spherical effect that can be directly impacted by the ablation profile of the corneal higher order aberrations yields a mathematical based surgical plan for the suggested treatment of the patient's refractive spherical magnitude, the astigmatic magnitude, and the astigmatic axis. Consequently, it is anticipated that Phoreides will prove to be a powerful surgical planning tool directly resulting in improved postoperative patient satisfaction with visual acuity and visual symptoms.

The decision to choose between a Phorcides derived Contoura LASIK ablation versus other various refractive procedures often times can be a difficult decision because of a lack of previous research analyzing patient satisfaction with their postoperative uncorrected visual acuity and visual symptoms. The purpose of this study is to determine the percentage of subjects satisfied with vision after Phorcides Planned Contoura LASIK.

6. OBJECTIVE(S)

To determine the percentage of subjects satisfied (Completely Satisfied or Very Satisfied) with vision after Phoreides Planned Contoura LASIK.

7. SUBJECTS

7.1. Subject Population

Eligible test subjects will be 21 to 39 years of age or older and who are interested in and appropriate candidates for LASIK.

A total of 104 eyes of 52 subjects at one site will be enrolled. Both eyes of a subject must be enrolled. Subjects must meet the inclusion criteria. Prior to enrollment, subjects will be provided information on the study and asked to sign a patient information and consent form to participate. The patient information and consent form will be approved by an appropriate ethics committee.

7.2. Inclusion Criteria

Subjects are eligible for the study if they meet the following criteria:

Note: Ocular criteria must be met in both eyes.

- Appropriate candidate for uncomplicated bilateral LASIK surgery
- Gender: Males and Females.
- Age: 21 to 39 years of age.

- Refractive error range SE refractive errors up to 0.00 to -9.00 D with maximum cylinder up to 3.00 D and sphere \leq -8.00 D.
- If currently wearing contact lenses:
 - Soft CTL wearers discontinue for minimum 3 days
 - o RGP CTL wearers discontinue for 1 month per decade of wear
 - Stable refraction (2 consecutive manifest refractions within 0.25 SE)
 - Stable K readings (2 consecutive K readings in 2 consecutive visits)
- Residual bed thickness 250µm or greater
- Willing and able to comply with scheduled visits and other study procedures.
- Pre-surgery BCDVA of 20/20 (0.00 logMAR) or better in each eye.

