11. SAMPLE SIZE JUSTIFICATION

We estimate that the study would require a sample size of 46 subjects (number of pairs) to achieve a power of 90% and a level of significance of 5%, for detecting a mean of difference of 25 points in satisfaction (using the PROWL questionnaire) between pairs, and assuming the standard deviation of the differences to be 50 points.³ To account for dropout, 52 subjects will be enrolled.

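### The sphere limit in Section 7.2, applied as printed, makes most of the stated SE range unreachable, and no cylinder convention is given to settle eyes near the limits

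*Combined protocol and SAP*

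**What the plan says.** The refractive criterion in Section 7.2 (Inclusion Criteria) puts three limits in one line: "Refractive error range SE refractive errors up to 0.00 to -9.00 D with maximum cylinder up to 3.00 D and sphere", followed by a less-than-or-equal sign and -8.00 D. The sphere limit carries a minus sign and has no wording about magnitude. The cylinder limit carries no sign.

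The section also says "Ocular criteria must be met in both eyes", so one eye decides the subject. Section 9.1 bars enrolment of anyone who does not meet the criteria, and Section 9.2.1 has each subject compared with them at qualification. Section 9.3.1 (Manifest Refraction) asks for sphere, cylinder and axis but names neither plus- nor minus-cylinder notation. No other section restates or explains the sphere limit.

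The population is described broadly. Section 7.1 refers to subjects "who are interested in and appropriate candidates for LASIK", and Section 3 to appropriate candidates for laser refractive surgery. Neither mentions high myopia.

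On age, Section 7.1 opens with "Eligible test subjects will be 21 to 39 years of age or older", while Sections 3 and 7.2 give a closed range of 21 to 39.

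**The concern.** With signed values, a sphere of -8.00 D or less means at least 8 D of myopic sphere. The same sentence opens with an SE range that starts at 0.00 D. A reader who applies the printed symbol gets a narrow, highly myopic group. A reader who takes it as a ceiling gets something close to the full SE range. The two readings share only eyes with sphere exactly -8.00 D.

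What is at stake is a clear definition of who is eligible. The primary result is a single-arm percentage of satisfied subjects with no control group, so its interpretation depends on knowing which refractions could enter. The criterion is an enrolment threshold that staff must apply, not background text.

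**Working it through.** The plan gives no figure that can be reproduced here, so the check applies the three limits together.

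**Inputs (Section 7.2).** SE from 0.00 to -9.00 D; cylinder magnitude at most 3.00 D; sphere limit -8.00 D.
**Assumptions.** SE = sphere + cylinder/2. Refractions lie on a 0.25 D grid. Both cylinder notations are tried, because none is stated. On this grid the SE and cylinder limits alone allow 475 sphere-cylinder combinations in either notation.

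**Reading A: sphere ≤ -8.00 D, as printed**

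- *Minus-cylinder (cylinder -3.00 to 0.00).* The weakest SE is -8.00 + 0.00/2 = -8.00 D, and the SE limit stops at -9.00 D. Eligible SE is -9.00 to -8.00 D, with sphere -9.00 to -8.00 D. This is 1.00/9.00 = 11% of the SE range and 25/475 = 5.3% of the combinations.
- *Plus-cylinder (cylinder 0.00 to +3.00).* The weakest SE is -8.00 + 3.00/2 = -6.50 D. The strongest sphere is -9.00 - 3.00/2 = -10.50 D. Eligible SE is -9.00 to -6.50 D. This is 2.50/9.00 = 28% of the SE range and 101/475 = 21.3% of the combinations.

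Under either notation, every eye with SE weaker than -6.50 D fails, although the sentence lists SE from 0.00 D. These percentages are shares of a dioptre range or a grid, not of patients.

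**Reading B: myopic sphere no stronger than -8.00 D**

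- *Minus-cylinder.* The whole SE range can be reached (459 of 475 combinations). The far end is reached at sphere -8.00 with cylinder -2.00: -8.00 - 2.00/2 = -9.00 D.
- *Plus-cylinder.* With cylinder at or above zero, SE cannot be stronger than the sphere, so it stops at -8.00 D (387 of 475 combinations). The -9.00 D limit never binds.

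**Same eye, two notations.** Transposing adds the cylinder to the sphere and reverses the cylinder's sign.

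| Minus-cylinder | Plus-cylinder | SE | Reading A | Reading B |
|---|---|---|---|---|
| -8.00/-2.00 | -10.00/+2.00 | -9.00 D | passes in both | passes in minus, fails in plus |
| -6.00/-2.00 | -8.00/+2.00 | -7.00 D | fails in minus, passes in plus | passes in both |

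Both eyes satisfy the SE and cylinder limits. Whichever direction is intended, some eyes change status with the notation alone.

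**Other end of the sphere range.** Reading B also leaves the weak end of the sphere range unprinted. In minus-cylinder notation +1.50/-3.00 has SE 1.50 - 3.00/2 = 0.00 D and would qualify. This is a further reason to state both ends.

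**The case against.** The strongest reply is that the sentence has a coherent meaning in context. It speaks of amounts up to a limit, gives the cylinder without a sign, and sits in a protocol that nowhere describes a high-myopia study. Read as a ceiling, the sphere limit fits the SE range exactly in minus-cylinder notation, and site staff would probably read through the slip. The public text was also read from PDF by a program and contains visible misreadings (the planning software's name is spelled two ways), so the symbol itself may be a transcription error. These points stand as reasons to think it a slip. They do not supply the missing cylinder convention, and they leave an enrolment threshold that says something else as printed.

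Three stronger readings are tempting, and the documents do not support them:

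- *That the rule contradicts itself and cannot be followed.* The limits overlap. In either notation some eyes satisfy all three, so the rule can be applied literally; it just selects a narrow group.
- *That low and moderate myopes will be audit deviations, or be declared ineligible afterwards.* No section says so. The investigator's power in Section 7.3 to declare a patient ineligible or nonevaluable rests on medical evidence of unsuitability, which a notation dispute is not. The refractions actually treated would also be visible, because manifest refraction is recorded preoperatively and Section 10.2 calls for summaries at all measurement time points.
- *That the age phrase in Section 7.1 is a second conflict of equal weight.* Section 7.1 itself requires subjects to meet the inclusion criteria, and Sections 3 and 7.2 agree on 21 to 39. The open-ended tail is a stray phrase.

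**Conclusion.** The point holds as a drafting fault in an operative criterion. As printed, the sphere limit reduces the eligible SE range from 9.00 D to 1.00 D (minus-cylinder) or 2.50 D (plus-cylinder), which does not match the general LASIK population described. Reversing the direction would remove most of that conflict, but eligibility near the limits would still depend on an unstated cylinder convention.

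This rests on the printed symbol being the one in the source document, on the usual definition of SE, and on the three limits applying jointly, which the sentence implies but does not say. If the symbol proves to be a misreading, the question of notation remains.

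No effect on the sample size or analysis is shown: the Section 11 calculation uses a mean difference, a standard deviation, power and alpha, none of which depends on refraction. This review does not say which refractive limit is right; that is for the sponsor to state.

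**What to change.** The sponsor should:

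1. Check the sphere symbol in Section 7.2 against the source document.
2. Reconcile the sphere, cylinder and SE limits, writing each as an explicit from-to interval with signs.
3. Name the cylinder convention in Section 7.2, repeat it in Section 9.3.1, and state that all three limits apply jointly.
4. Build the same checks into the eligibility CRF, so that every eye is tested in one notation.
5. As a minor tidy-up, make the age wording in Section 7.1 agree with Sections 3 and 7.2.

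This is best done before the first subject is qualified. If enrolment has begun, the sponsor should record which reading and which notation the site has used. The cost is a one-line protocol correction with a matching CRF check; no change to the sample size or the analysis is needed.
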